1.1 Synopsis

Protocol Title: Open-Label 4-Period Dose-Escalation Safety and Efficacy Study of AD313 in Participants With Obstructive Sleep Apnea

Sponsor Study Name.: SEED

Sponsor: Apnimed, Inc.

Rationale:

Selective norepinephrine reuptake inhibitors (SNRIs) such as atomoxetine are thought to improve obstructive sleep apnea (OSA) by increasing pharyngeal muscle stiffness and responsiveness.

Cannabinoids, including dronabinol, also have shown potential for reduction of OSA severity. The mechanism of beneficial action of dronabinol appears to be distinct from that of SNRIs, potentially involving stabilization of respiratory patterns and increased activation of upper airway dilating muscles during sleep.

The SEED study is designed to assess the safety and efficacy for OSA of 3 escalating dose combinations of atomoxetine with dronabinol, compared to baseline and to atomoxetine alone.

Overall Design:

The SEED study is an open-label, 4 consecutive period dose-escalation study of combinations of atomoxetine with dronabinol vs. atomoxetine alone in participants with moderate- to severe OSA. A screening polysomnogram (PSG) will be conducted to establish that each participant meets study enrollment criteria and to serve as baseline. Each participant will then receive escalating doses of atomoxetine, then escalating doses of the combination of atomoxetine with dronabinol, as follows:

- Week 1: atomoxetine 40 mg x 3 days, then atomoxetine 80 mg x 4 days
- Week 2: atomoxetine 40 mg/dronabinol 2.5 mg
- Week 3: atomoxetine 80 mg/dronabinol 5 mg
- Week 4: atomoxetine 80 mg/dronabinol 10 mg

Dosing of study drug occurs at the participants usual bedtime. Dose escalation will be based on safety and tolerability, as assessed at weekly clinic visits and telephone contact with participants mid-week of each dosing period.

In addition to the screening/baseline PSG, three on-drug PSGs will be conducted on the final night of the following dosing periods:

- 1st week, dosing atomoxetine 80 mg alone
- 3rd week, dosing atomoxetine 80 mg/dronabinol 5 mg
- 4th week, dosing atomoxetine 80 mg/dronabinol 10 mg

Number of Participants:

A total of 15 participants will be enrolled.

Study Duration:

The overall study duration will be up to 9 weeks, as follows:

- Screening, up to 3 weeks;
- Atomoxetine alone: 1 week
- Dronabinol dose escalation period: 3 weeks
- End of Study telephone contact: 2 weeks

1.2 Schedule of Activities (SoA)

Table 1 Schedule of Activities

Procedures	Non-PSG Screening V1	Screening/ Baseline PSG V2	Dosing Period								EoS Call	
			ATO 40 3d, ATO 80 4d		ATO 40/DRO 2.5		ATO 80/DRO 5		ATO 80/DRO 10			
			At home dosing	V3 PSG	At home dosing	V4	At home dosing	V5	At home dosing	PSG V6		
Day ¹	-21 to -1		1 - 7 ± 1	7 ± 1	8-14 ± 2	14 ± 2	15 – 21 ± 2	21 ± 2	21-28 ± 2	28 ± 2	42 ± 2	
Informed consent	X											
Demography	X											
Physical exam	X											
Medical history	X											
Pregnancy test ²	X											
Clinical laboratory testing	X											
12 Lead ECG	X											
PSG		X ³		X				X		X		
Study drug dispense/return		X		X		X		X		X		
HS study treatment ⁴			↔	↔	↔	↔	↔	↔	↔	↔		
PGI-S, PROMIS sleep impairment, PROMIS sleep disturbance, PROMIS fatigue, DSST, VOLT, PVT ⁵		X		X				X		X		
Vital signs ⁶	X	X		X		X		X		X		
AE/SAE monitoring ⁷			↔	↔	↔	↔	↔	↔	↔	↔	↔	
Prior/concomitant medication			↔	↔	↔	↔	↔	↔	↔	↔	↔	

Abbreviations: AE = adverse event; ATO = atomoxetine; DRO = dronabinol; DSST = Digit symbol substitution test; ECG = electrocardiogram; HS = Hora Somni; PGI-S = patient global impression of severity of OSA; PSG = polysomnography; SAE = serious adverse event; SAQI = Sleep Apnea Quality of Life Index; WOCBP = women of childbearing potential; PROMIS = Patient Reported Outcomes Measurement Information System; PVT = psychomotor vigilance test; VOLT = visual object learning task

¹Study days shown represent case with no use of ± window days; study days shift cumulatively if window days are used

² WOCBP only

³ On a case-by-case basis with agreement of Sponsor a PSG conducted at the site within 3 months may be used instead of the Screening PSG

⁴ Study medication administered at lights out; dose on PSG nights is from supply dispensed to the participant if available, but can be provided from separate site supply.

⁵ Administered at similar time on morning of each PSG visit

⁶ Vital signs include seated blood pressure in triplicate, pulse, respiratory rate; vital signs on PSG nights taken morning after PSG.

⁷ Site contacts participant by telephone mid-week of each at-home dosing period for safety evaluation and reminder of study activities

2 Introduction

2.1 Study Rationale

Selective norepinephrine reuptake inhibitors (SNRIs) such as atomoxetine are thought to improve obstructive sleep apnea (OSA) by increasing pharyngeal muscle stiffness and responsiveness (1-4).

Cannabinoids, such as dronabinol, have shown potential for reduction of OSA severity (21). The mechanism of beneficial action of dronabinol appears to be distinct from that of SNRIs, potentially involving stabilization of respiratory patterns and increased activation of upper airway dilating muscles during sleep.

The SEED study is designed to assess the safety and efficacy for OSA of 3 escalating dose combinations of atomoxetine and dronabinol.

2.2 Background

2.2.1 Obstructive Sleep Apnea

The National Commission on Sleep Disorders Research identified sleep disorders as a major public health burden. OSA is the most common and serious of these sleep disorders and affects approximately 20 million people in the United States (US), with approximately 13% of men and 6% of women affected (5). OSA is characterized by repetitive collapse or ‘obstruction’ of the pharyngeal airway during sleep, manifesting as repetitive episodes of hypopnea (i.e., shallow breathing) or apnea (i.e., paused breathing). These episodes of hypopnea or apnea may lead to arousal from sleep, sleep fragmentation, excessive daytime sleepiness, and/or neuropsychological impairment.

Research has shown that a number of pathogenic factors, or traits, contribute to the development of OSA (6-9). The most important factors are the presence of an anatomically small, collapsible upper airway and a loss of pharyngeal muscle tone or responsiveness during sleep.

Long-term, OSA is associated with increased mortality and a number of adverse cardiovascular, neurocognitive, metabolic, and daytime functioning consequences (10-19).

2.2.2 Unmet Medical Need

Treatment for OSA changed little over the past 40 years, with the overwhelming majority of patients treated with positive airway pressure, the most common of which is continuous positive airway pressure (CPAP), provided by a machine that mechanically maintains an open airway.

Other treatments, such as pharyngeal surgery, mandibular advancement devices, and implantable nerve stimulators, were developed to address the anatomical predisposition to collapse; however, they have shown limited efficacy for niche populations.

While CPAP and related therapies are effective in improving sleep characteristics and oxygenation, many, perhaps most, patients find these devices uncomfortable or intolerable, and most estimates indicate that fewer than 50% of patients prescribed CPAP use it more than 4 hours per night, if at all (20). Efforts to develop pharmacologic therapies, such as antidepressants, stimulants, and hormonal agents, for the treatment of OSA have been ongoing for at least 20 years, with no success thus far.

As many patients cannot use CPAP because they find it intolerable, this represents a significant health concern, as OSA is associated with numerous co-morbidities and increased mortality. Alternative options, such as drugs that activate the pharyngeal muscles, are needed.

2.2.3 Biological Rationale

Atomoxetine is a pre-synaptic norepinephrine reuptake inhibitor indicated for the treatment of attention deficit hyperactivity disorder in children and adults. Dronabinol is synthetic delta-9-tetrahydrocannabinol (delta-9-THC) indicated for the treatment of anorexia in patients with AIDS and nausea and vomiting associated with cancer chemotherapy. Apnimed believes that the combination of dronabinol and atomoxetine may have an improved efficacy profile in patients with OSA compared to either constituent alone.

3 Endpoints

	Endpoints
Primary	
• AHI4%, ATO 80/DRO 10 vs. baseline
Secondary	
• AHI4%, ATO 80/DRO 10 vs. ATO 80• AHI4%, ATO 80/DRO 5 vs. baseline• AHI4%, ATO 80/DRO 5 vs. ATO 80• HB4%, ODI4%, Total time with $\text{SaO}_2 < 90\%$, Proportion of participants with $\geq 50\%$ reduction in AHI4%, HB4%, ODI4%
Exploratory	
• PGI-S• PROMIS sleep impairment• PROMIS sleep disturbance• PROMIS fatigue• AHI4%, highest dose achieved by patient (ie ATO 80/DRO 5 or ATO 80/DRO 10 vs. baseline and vs. ATO 80)• AHI3 (hypopnea scored when associated with 3% O_2 desaturation)• AHI3a (hypopnea scored when associated with 3% O_2 desaturation or arousal)• OSA endotype endpoints (Vpassive, Vactive, Muscle Compensation, Loop Gain)• PSG sleep and arousal parameters
Safety Endpoints	
• Vital signs, Spontaneous adverse events, DSST, VOLT, PVT

Abbreviations: AHI = apnea-hypopnea index; ATO = atomoxetine; DSST = digit symbol substitution test; DRO = dronabinol; HB = hypoxic burden; ODI = Oxygen Desaturation Index; OSA = obstructive sleep apnea; PROMIS = Patient Reported Outcome Measurement Information System; PGI-S = Patient Global Impression of Severity; PSG = polysomnography; PROMIS = Patient Reported Outcome Measurement Information System; PVT = psychomotor vigilance task; SaO_2 = oxygen saturation; SAQLI = Sleep Apnea Quality of Life Index; VOLT = visual object learning task

4 Study Design

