8.1 Sample Size Determination

In Apnimed studies atomoxetine alone has decreased AHI by 65% or more, and dronabinol has been reported to decrease AHI by about 50% (21). Assuming that 12 participants will complete the trial, the study will have 90% power to detect a treatment difference with baseline at a two-sided 0.05 significance level if the true difference is AHI is 12 units and the within-subject standard deviation 12. Considering an attrition rate of 25%, we will enroll 15 participants to complete the study.

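### Does the ≥50% responder endpoint need changing, given that Section 8.1 credits each drug alone with a reduction that size and no comparator is named?

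*Combined protocol and SAP*

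**What the plan says.** In the endpoint table of Section 3, each secondary AHI4% line names a dose and a comparator, for example "AHI4%, ATO 80/DRO 10 vs. ATO 80". There are three such lines: the higher combination dose against atomoxetine 80 mg, and the middle dose against baseline and against atomoxetine 80 mg. The fourth secondary bullet is built differently. It runs "HB4%, ODI4%, Total time with" low oxygen saturation, and then the proportions of participants with at least a 50% "reduction in AHI4%, HB4%, ODI4"%. It gives no dose, visit or comparator. Section 8 (sample size, populations, interim analyses) does not supply them.

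The synopsis states a two-part aim: the combinations are assessed "compared to baseline and to atomoxetine alone". It also says the screening PSG is used "to establish that each participant meets study enrollment criteria and to serve as baseline". Section 2.2.3 states the sponsor's belief that the combination "may have an improved efficacy profile in patients with OSA compared to either constituent alone". Section 8.1 gives the component effects: "In Apnimed studies atomoxetine alone has decreased AHI by 65% or more, and dronabinol has been reported to decrease AHI by about 50"%. It powers the primary comparison with baseline on 12 completers "if the true difference is AHI is 12 units and the within-subject standard deviation 12".

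On-drug PSGs are scheduled at Visit 3 (atomoxetine 80 mg alone), Visit 5 (80/5) and Visit 6 (80/10), in the same participants (Sections 1.2 and 4.1).

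**The concern.** A 50% cut lies below the reduction that Section 8.1 expects from atomoxetine alone and equals the one it reports for dronabinol. Someone who reaches 50% on the combination may well have reached it on atomoxetine at Visit 3. If the responder rate were reported only against baseline, a high figure could be taken as a benefit of adding dronabinol when most of it belongs to atomoxetine.

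The silent bullet adds to the worry. Two analysts could choose different doses or comparators, and could choose after seeing the data. For hypoxic burden (HB4%) and the desaturation index (ODI4%) the documents give no component figures, so Visit 3 is the only internal reference. At stake is the reading of several secondary results. The primary endpoint is not affected.

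**Working it through.** **Plan's own figure.** Section 8.1 claims 90% power with n = 12, difference 12, SD 12 and two-sided alpha 0.05. Taking 12 as the SD of the within-participant difference, a paired t-test has 88.3% power and the normal approximation gives 93.4%. The stated figure is reproduced closely enough, and that reading of the SD is carried forward.

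**Cut against component effects.** 50% < 65% (atomoxetine); 50% ≈ 50% (dronabinol). The textual observation is correct.

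**Expected AHI4% responders on atomoxetine alone.** Inputs: 65% mean reduction and SD 12 (Section 8.1), baseline AHI B from 10 to 50 (Section 5.1). A responder has a reduction of at least 0.50B, so

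P = Φ((0.65B − 0.50B)/12) = Φ(0.15B/12).

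- B = 10: Φ(0.125) = 55.0%
- B = 25: Φ(0.3125) = 62.3%
- B = 50: Φ(0.625) = 73.4%

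In 12 participants, 55.0% to 73.4% is 6.6 to 8.8 responders. If the SD of the difference were 12√2 ≈ 17, the range would be 53.5% to 67.1%.

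Higher rates need something the documents do not fix. A log-normal ratio with median 0.35 gives Φ(ln(0.50/0.35)/s), which is 88.3% at s = 0.3, but no such spread is stated. Section 8.1 does allow reductions above 65%: a 75% reduction at B = 50 gives Φ(0.25 × 50/12) = 85.1%.

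**What 12 completers can show.** Exact (Clopper-Pearson) 95% intervals:

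| Responders | 95% CI |
|---|---|
| 0/12 | 0 to 26.5% |
| 1/12 | 0.2 to 38.5% |
| 2/12 | 2.1 to 48.4% |
| 9/12 | 42.8 to 94.5% |
| 10/12 | 51.6 to 97.9% |
| 11/12 | 61.5 to 99.8% |
| 12/12 | 73.5 to 100% |

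The 12/12 lower limit is 0.025^(1/12) = 73.5%, just above 73.4%. So on the documented inputs a perfect result clears the range, though barely, and 11/12 does not. If the atomoxetine-alone rate could be as high as 85% or 88%, even 12/12 would not clear it. At the other end, 0, 1 or 2 of 12 would lie wholly below 55%. It is therefore not true that no result could separate the combination from atomoxetine alone. What holds is that a high result would rarely do so.

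**Paired comparison with Visit 3.** An exact McNemar test with all changes in one direction gives p = 2 × 0.5^5 = 0.063 for five converts and 2 × 0.5^6 = 0.031 for six. Expected Visit 3 non-responders number 12 × 0.450 = 5.4 down to 12 × 0.266 = 3.2 on the documented inputs, fewer than the six needed. Naming atomoxetine 80 mg as comparator for the responder proportion would therefore not turn it into a useful test of dronabinol.

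**Where the plan addresses dronabinol's contribution.** Section 3 contrasts AHI4% with atomoxetine 80 mg at 80/10 and at 80/5 as secondary, and at the highest dose achieved as exploratory. These are within-participant comparisons on the continuous measure, which keep information that a dichotomy discards.

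**The case for a change.** The strongest case for a change is that the gap is real and cheap to close. The bullet is less specific than its neighbours and even than the exploratory highest-dose line, which names both comparators. A sentence would fix the doses and comparators, define reduction as from the Visit 2 baseline, and call for Visit 3, 5 and 6 counts side by side. The concern also survives without any assumed upper end: only a perfect score clears 55% to 73.4%, and only by 0.1 point. With the plan's 25% attrition from 15 enrolled, about 11 complete (15 × 0.75 = 11.25), and then even 11/11 has a lower limit of 0.025^(1/11) = 71.5%, below 73.4%.

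The arithmetic stands, and so does the observation about the bullet. But the arithmetic tests an inference the plan never proposes: no responder success criterion, reference rate or hypothesis test appears anywhere. Baseline-only reporting is itself a reading of a silent line. A responder rate against baseline also properly serves the first half of the synopsis aim. Nor is the cut plainly undemanding on the plan's own terms: the 12-unit planning difference is less than a 50% reduction for any baseline above 12/0.50 = 24, and only 12/50 = 24% at baseline 50. Finally, the clarifying sentence would leave the cut, visits, sample size and primary endpoint as they are, and the resulting table would still not test dronabinol.

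**Conclusion.** No change to the plan is needed. Two observations are correct: the 50% cut is at or below the AHI effect credited to each drug alone, and one secondary bullet names no dose, visit or comparator. On a 65% reduction, SD 12 and baseline AHI 10 to 50, about 55% to 73% of participants would respond on atomoxetine alone, so a combination AHI4% responder rate cannot by itself be credited to dronabinol. That range rests on a normal spread with SD 12 for the difference. It moves up with a larger reduction or a tighter spread, neither of which the documents specify, and no corresponding range can be derived for HB4% or ODI4%.

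This is a gap that analysts fill sensibly. The synopsis designates the baseline PSG, the AHI4% lines set the pattern of contrasts, and Visits 3, 5 and 6 provide the values for a side-by-side descriptive display. The comparison that bears on dronabinol, AHI4% against atomoxetine 80 mg, is already prespecified at both combination doses measured by PSG and is unaffected. What remains is a caution for interpretation: read the combination responder rate beside the Visit 3 rate, as description.

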4.1 Overall Design

The SEED study is an open-label, 4 consecutive period dose-escalation study of combinations of atomoxetine and dronabinol in participants with moderate to severe OSA. Participants will undergo initial pre-screening to determine potential study eligibility. Participants selected for further screening should either have a previous history of OSA of a severity consistent with enrollment criteria or be at high risk (e.g. as assessed by STOP-Bang Questionnaire score). Only participants who meet all non-PSG enrollment criteria at Visit 1 are eligible for a screening PSG. On a case by case basis and with agreement of the Sponsor a PSG conducted at the site within 3 months may be used instead of the Screening PSG.

Participants who meet all enrollment criteria will receive an escalating dose of atomoxetine the first week: 3 days of atomoxetine 40 mg followed by 4 days of atomoxetine 80 mg. Participants will then receive escalating dose combinations of atomoxetine and dronabinol for the next 3 weeks. The weekly dose schedule is as follows:

- Week 1: atomoxetine 40 mg x 3 days, then 80 mg x 4 days
- Week 2: atomoxetine 40 mg/dronabinol 2.5 mg
- Week 3: atomoxetine 80 mg/dronabinol 5 mg
- Week 4: atomoxetine 80 mg/dronabinol 10 mg

Dose escalation will be based on safety and tolerability, as assessed at weekly clinic visits and by telephone contact with participants mid-week of each at-home dosing period. Patients who do not tolerate dose escalation will discontinue dosing.

Three on-drug PSGs will be conducted on the final night of the following dosing periods:

- 1st week, dosing atomoxetine 80 mg alone
- 3rd week, dosing atomoxetine 80 mg/dronabinol 5 mg
- 4th week, dosing atomoxetine 80 mg/dronabinol 10 mg

Study drug for Week 1 is dispensed to participants at Visit 2.. Any unused Week 1 study drug is returned at Visit 3. Similarly, study drug for Week 2, 3, and 4 is dispensed at Visits 3, 4 and 5, and unused study drug similarly returned at the subsequent visit.

Dosing of the study treatment will occur each night at the participant's usual bedtime, both during at-home nights and Visit 3, Visit 5 and Visit 6 PSG nights. Study drug dose on PSG nights

[figure not shown]
is from the supply dispensed to the participant if available, but can be provided from separate site supply.

The morning of each PSG the PGI-S, PROMIS assessments, DSST, VOLT and PVT will be administered.

An End-of-Study phone call will take place 2 weeks following the end of study drug dosing.

Participants who discontinue from the study will not be replaced. No subsequent open-label extension is planned following the study.

Figure 1: Overview of Study Design

EoS = End of Study; PSG = polysomnography; 40 = atomoxetine 40 mg alone; 80 = atomoxetine 80 mg alone; 40/2.5 = atomoxetine 40 mg/dronabinol 2.5 mg; 80/5 = atomoxetine 80 mg/dronabinol 5 mg; 80/10 = atomoxetine 80 mg/dronabinol 10 mg

4.2 Scientific Rationale for Study Design and Dose

Selective norepinephrine reuptake inhibitors (SNRIs) such as atomoxetine are thought to improve obstructive sleep apnea (OSA) by increasing pharyngeal muscle stiffness and responsiveness.

Cannabinoids, including dronabinol, also have shown potential for reduction of OSA severity (21). The mechanism of beneficial action of dronabinol appears to be distinct from that of SNRIs, potentially involving stabilization of respiratory patterns and increased activation of upper airway dilating muscles during sleep. Cannabinoids have also shown a hypnotic effect that may counteract the potential wakefulness induced by atomoxetine.

This study is designed to investigate if the combination of atomoxetine and dronabinol is safe and effective in participants with moderate to severe OSA.

4.3 End of Study Definition

A participant is considered to have completed the study if he/she has completed all phases of the study through the last scheduled procedure shown in the Schedule of Activities (SoA).

The end of the study is defined as the date of the last visit of the last participant in the study or last scheduled procedure shown in the SoA for the last participant in the study globally.

5 Study Population

Eligible participants will be recruited both from the existing clinic population at the study site, including databases of previous subjects who participated in other studies, and through direct advertising to the community.

Participants must be able to provide written consent and meet all the inclusion criteria and none of the exclusion criteria.

5.1 Inclusion Criteria

Age and Sex

1. 25 to 65 years of age, inclusive, at the Screening Visit.

Disease Measures

2. AHI 10 to 50 (hypopneas defined by 4% oxygen desaturation)
3. $\leq 25\%$ of apneas are central or mixed apneas at V2 baseline PSG

Weight

4. BMI between 18.5 and 40.0 kg/m², inclusive, at the pre-PSG visit.

Male participants:

5. If male and sexually active with female partner(s) of childbearing potential, participant must agree, from Study Day 1 through 1 week after the last dose of study drug, to practice

the protocol specified contraception (see Appendix 4: Contraceptive Guidance and Collection of Pregnancy Information).

Female participants:

6. If a woman of childbearing potential (WOCBP), the participant must agree, from Study Day 1 through 1 week after the last dose of study drug, to practice the protocol specified contraception (See Appendix 4: Contraceptive Guidance and Collection of Pregnancy Information). All WOCBP must have negative result of a serum pregnancy test performed at screening.
7. If female and of non-childbearing potential, the participant must be either postmenopausal (defined as age ≥ 55 years with no menses for 12 or more months without an alternative medical cause) or permanently surgically sterile (bilateral oophorectomy, bilateral salpingectomy or hysterectomy).

Informed Consent

8. Participant voluntarily agrees to participate in this study and signs an Institutional Review Board (IRB)-approved informed consent prior to performing any of the Screening Visit procedures.
9. Participant must be able to understand the nature of the study and must have the opportunity to have any questions answered.

